4.5. Randomisation Procedure

All subjects that meet the inclusion and exclusion criteria will be randomised to one of two treatment arms. Each arm examines the non-CE marked investigational product and one of the CE marked comparator investigational products in the following order:

- Arm A: The non-CE marked investigational product, then one of the five CE marked comparators investigational products.
- Arm B: One of the five CE marked comparators investigational products, then the non-CE marked investigational product.

There will be one randomisation list for the subjects normally using a 1-piece product and one for subjects normally using a 2-piece product. This is to stratify the two types of subjects to the treatment arms. The randomisations list will consist of blocks of ten, and centralised.

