In light of the data obtained it might be considered to make additional explorative analyses based on a subset of the ITT/PP population.

Analysis of the primary endpoint

Max itching score within a week at steady state will be analysed by a mixed repeated measures model using individual week max scores (on a scale from 0-10) as the observational unit. The model will consider that observations corresponding to different subjects are independent; whereas observations corresponding to the same subject are correlated. The correlation between observations corresponding to the same product can be larger than observations corresponding to different products. Hence the model includes a fixed effect of product (comparator product, test product), a fixed effect of product type (1- or 2-pc), a fixed interaction between product and product type, a fixed period effect, an interaction between period and product, a random effect of subject and a random interaction effect of product and subject.

The model might be reduced by removing non-significant fixed effects, if relevant. The interaction between period and product allows for a possible carry-over effect. It is assumed that a possible carry-over effect is the

CONFIDENTIAL

same for 1- and 2-pc users. If the interaction is significant, data from only the first test period will be analysed as a parallel arm study because the first period is free of carry-over effects and period will be excluded from the model.

All combinations of differences between the two products will be estimated for both 1- and 2- pc products. Furthermore, differences for same product between product types will be estimated (if the model is not reduced).

Analysis of the secondary endpoints

The endpoints regarding pain, burning, physical discomfort, ability to move around and the overall ability to stick the baseplate to the skin (on a scale from 0-10) will be analysed by the same model as the primary endpoint starting by calculating the max within a week at steady state.

[REDACTED] endpoints regarding bleeding (Y/N), experiencing any weeping or moisture (Y/N) and Ulcers or sores (Y/N) per baseplate change at steady state will be analysed by a repeated logistic regression model with the same effects included as for the primary endpoint.

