11.2. Sample size

The itching score is given at each baseplate change and the max of these scores per week at steady state is the primary endpoint. The max score is only calculated if there are measurement for more than four days within a week. For each subject approximately three measurements will be available for each test period.

The sample size calculation is based on a simplified linear mixed model with only 1-pc users and no period effect (corresponding to the design from CP300). The model includes a fixed effect of product (comparator and test product), a random effect of subject and a random interaction effect of product and subject.

Based on data from CP300 it is assumed that the total standard deviation of the primary endpoint is 1.82 and that the total variation 1.82² is divided so that:

- a random effect of subject accounts for 68% of the total variation
- a random interaction effect of product and subject accounts for 0%
- and the residual accounts for 32% of the total variation

In table 1 the needed sample size is calculated by simulation for varying values of the true difference between comparator and test product regarding mean max itching score per week and for different values of the power to demonstrate that the difference is significantly different from 0.

Table 4: Subjects needed for comparing mean max itching score between two products

True difference	Reduction in mean if the mean for the comparator is 2.2 as for [REDACTED] in CP300	Power		
		0.8	0.85	0.9
0.6	27%	46	>46	>46
0.7	32%	35	40	45
0.8	36%	30	32	36

Based on the numbers in the table, 40 subjects should test each product to ensure a power of 85%, if the true difference between the comparator product and a test product is 0.7 (corresponding to a 32% reduction if the mean for the comparator is 2.2 as in CP300). This will be enough when comparing the two products. 1-pc and 2-pc users will be evaluated separately (in a combined model). As there are no previous data for 2-pc users the sample size calculations for 1-pc users is assumed to cover 2-pc users as well. To take a potential drop-out (20%) into account it is recommended to include a total of 48 1-pc and 48 2-pc users, resulting in a total of 96 subjects.

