If a carry-over effect is present and therefore data from only the first period is analysed as a parallel arm trial 40 subjects (20 in each arm) will ensure a power of 82% if the true difference between the comparator product and the test product is 1.7. If there are no significant difference between 1- and 2-pc users, 80 subjects (40 in each arm) will ensure a power of 83% if the true difference between the comparator product and the test product is 1.2 (the difference in CP300 was estimated to 1.3).

The total number of 80 subjects is the required number of subjects for the [REDACTED]

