11.3. Level of significance and power

A significance level of 5% will be applied. For a description of the power see section 11.2 above.

CONFIDENTIAL

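### The primary model may be cut down on p-values, so the data can decide whether the primary answer is one pooled product difference or separate 1-piece and 2-piece differences

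*Combined protocol and SAP*

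**What the plan says.** Section 11.1 (Analysis of the primary endpoint) models the weekly maximum itching score. Besides product and product type, the fixed part contains "a fixed interaction between product and product type, a fixed period effect, an interaction between period and product". The reduction sentence follows: "The model might be reduced by removing non-significant fixed effects, if relevant". The plan does not say which effects may go, in what order, at what p-value, or when reduction counts as relevant.

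On the contrasts, the same section says "All combinations of differences between the two products will be estimated for both 1- and 2- pc products", with no condition attached. The next sentence makes only the comparison between types conditional: "differences for same product between product types will be estimated (if the model is not reduced".

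Section 11.2 arrives at 40 evaluable subjects, applies that figure to each type, and states "1-pc and 2-pc users will be evaluated separately (in a combined model". It also notes that no earlier data exist for 2-piece users. For the carry-over fallback, where only the first period is analysed, it foresees pooling: "If there are no significant difference between 1- and 2-pc users, 80 subjects (40 in each arm) will ensure a power of 83" per cent, at a true difference of 1.2.

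Section 4.5 gives each type its own randomisation list: "This is to stratify the two types of subjects to the treatment arms". On the error level, section 11.3 says only "A significance level of 5% will be applied". Section 11.1 calls the study exploratory and waives multiplicity adjustment. Section 11.4 counts one significant skin endpoint as success.

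**The concern.** Without the product-by-type term the model has a single product effect. The two by-type differences that section 11.1 promises are then identical by construction. A p-value therefore decides whether the primary result answers one question (does the product work on average over the types?) or two (does it work in each type?). A non-significant interaction does not show that the types respond alike, and the plan has no 2-piece data to support that assumption.

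At stake is what may be said about each type. If only one type benefits and the interaction is missed, the averaged effect is reported for both, and the type with no benefit gets a positive result. Section 11.1 reuses this model, or one close to it, for most secondary and several exploratory endpoints. Different endpoints could therefore be reduced differently, some pooled and some by type.

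**Working it through.** **Inputs.** From section 11.2: total SD 1.82; variance shares of 68% subject, 0% product-by-subject and 32% residual; true difference 0.7; 40 evaluable per type; about three weekly maxima per period. From section 11.3: 5%. Assumed, because not stated: two-sided tests, 20 subjects per sequence arm in each type, and removal at p ≥ 0.05.

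**1. Reproduce the plan's 40.** Residual variance = 0.32 × 1.82² = 1.06. With one score per period, n = 2 × 1.06 × (1.960 + 1.036)² / 0.7² = 39 by the normal formula, or 41 with the t distribution. Power at 40 is 84.3%. The stated 40 is reproduced, but only with one score per period; three independent scores would need 13 (normal) or 15 (t). Both settings are carried forward for that reason. The fallback powers also reproduce, at 82.1% and 83.0%.

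**2. Rule examined.** Keep product-by-type if p < 0.05 and test each type at 5%. Otherwise drop it, make one pooled 5% test, and read the result as covering both types.

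**3. No effect in either type.** With equal groups the pooled and interaction statistics are independent.
- One fixed pooled test: 5.0%.
- Two fixed by-type tests: 5% each; at least one, 1 − 0.95² = 9.75%.
- Reduction rule, any false finding: 0.95 × 0.05 + 0.05 × 0.65 = 0.0475 + 0.0325 = 8.0%. The 0.65 is the chance that at least one type is significant given a significant interaction (4 million normal draws).
- Reduction rule, a given type: 6.4%.

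A simulation of the two-sequence cross-over (100,000 trials) agrees: 8.1% and 6.5% with one score per period, 7.9% and 6.3% with three.

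**4. One type benefits, the other does not.** The SE of a by-type difference is √(2 × 1.06 / 40) = 0.230 with one score, or 0.230/√3 = 0.133 with three. The interaction statistic has mean difference/(SE × √2).

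| True difference in the other type | Scores per period | Interaction power (normal theory) | Type with no effect declared significant (simulated) |
|---|---|---|---|
| 0.7 | 1 | 0.7/0.326 = 2.15, so about 58% | 27% |
| 0.4 | 3 | 0.4/0.188 = 2.13, so about 57% | 27% |
| 0.7 | 3 | 0.7/0.188 = 3.72, so about 96% | 8% |

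Fixed by-type tests give 5% in every row. The first row can be checked by hand. The pooled statistic has the same mean, 2.15, so the chance of dropping the interaction and then finding the pooled test significant is about 0.42 × 0.58 = 0.24. The rest comes from trials that keep the interaction and find the null type significant by chance.

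**5. Power.** At 0.7 with one score per period, power is 84% by type (40 subjects) and 99% pooled (80 subjects). Reduction therefore changes both the question and the power.

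The carry-over pre-test is left out of these figures. Including it raises the rule's 8.0% to about 11%, but it also raises the fixed pooled test from 5% to about 8%, so most of that increase has another source.

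**The case against.** **Overall error.** A reader might infer that the rule inflates the trial's false-positive rate. That depends on the comparator. The 8.0% exceeds the 5% of one pre-specified pooled test but is below the 9.75% of the two unadjusted by-type tests that section 11.2 implies. The plan claims no familywise control in any case. This objection stands against a claim of overall inflation. It does not touch the error for a given type, nor the need to say which contrast is primary.

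**Free choice of result.** If an analyst could claim whichever of the pooled, 1-piece and 2-piece results was significant, the rate would be 11.5%. The plan gives no such licence, so that figure does not describe it.

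**Contradiction.** Sections 11.1 and 11.2 might be read as contradicting each other. The documents do not go that far. Section 11.2 itself foresees pooling on non-significance, though only in the first-period fallback, and section 11.1 promises both by-type differences unconditionally. This is an unresolved inconsistency.

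**Masking.** With a difference of 0.7 in one type only and one score per period, the interaction is missed about 42% of the time, and a common effect averaging 0.35 is reported. With the three weekly scores the plan expects, this falls to 4%. The larger figure should not be quoted alone. The risk returns at smaller differences, as the 0.4 row shows. Summaries by product type are planned in section 11.1 and would partly expose a difference, but they do not set the inferential result.

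**Period and product type.** The calculations concern only product-by-type. Product type is constant within a subject, so dropping its main effect should hardly move a mainly within-subject contrast. The reason to keep these two terms is that they belong to the design, not that a measured error follows from removing them.

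**Conclusion.** The point holds in this form: the reduction rule is unspecified and data-driven, and it leaves open whether the primary answer is pooled or by type, which sits badly with sizing each type at 40. With no effect anywhere, the error for a given type is 6.4% instead of 5%. When only the other type benefits, it is about 27% (0.7 with one score, or 0.4 with three independent scores) and about 8% at 0.7 with three. The main harm is a data-chosen estimand and a possible wrong conclusion for one type. The documents support neither overall inflation nor a flat contradiction.

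The figures rest on a 5% removal threshold, 40 evaluable per type, equal sequence arms, the variance shares in section 11.2, and a pooled result being read as applying to both types. If weekly maxima within a period are more correlated than the assumed 0% product-by-subject share implies, the three-score results move towards the one-score results.

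**What to change.** - Delete the reduction sentence in section 11.1, or confine it to a labelled sensitivity analysis.
- In the two-period analysis, always keep product type, product-by-type and period. In the first-period-only analysis, where period drops out, keep product type and product-by-type.
- Where period-by-product is retained, define the product difference as the average over the two periods.
- Name the 1-piece and 2-piece product differences as the primary contrasts, as sized in section 11.2. Read each at 5% for its own type, and state the 9.75% chance of at least one false finding under no effect. Report the type-averaged difference as secondary.
- Align the pooling remark in the section 11.2 fallback with this choice.
- Apply the same rule to every endpoint that reuses the model.

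This is a cheap improvement. It needs wording changes only, with no new subjects or data. The cost is a few degrees of freedom and less power than a pooled test (84% against 99% at 0.7 with one score per period), which the by-type sizing already accepts.

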4.3. Discussion of clinical investigation design

The open-label, randomised, controlled, comparative, cross-over design was selected for CP288 based on the following advantages:

Randomised:

- The randomisation ensures that the study effect, including selection bias and confounding covariates are adjusted for.

Cross-over:

- The influence of confounding covariates is reduced because each cross-over subject serve as his or her own control.
- Cross over design allows us to assess user preference as all users will try both the new non-CE marked product and one of five CE marked products
- Subjects are their own control and fewer subjects need to be included, even though the test period is longer.
- Requires fewer subjects than parallel designs.

Open label:

- The investigation is not blinded because the Coloplast investigational product and comparators are visibly different from each other.

Enrolment period:

- The duration of the test periods ($42^{\pm 3}$ days) and number of visits should be adequate to assess data on the wear time, leakage pattern, and skin condition of the subjects. The investigational products are tested for $42^{\pm 3}$ days to ensure that the skin will have time to adjust to new conditions, reach a steady state, and for the subjects to test an adequate number of products to give a thorough evaluation of the products.

To account for a possible carry-over effect the steady state period of the treatment period begins after three weeks of product use as it is anticipated that the skin has adapted to the new product after three weeks. The statistical analysis will evaluate if there are signs of a carry-over effect and take that into consideration when presenting the results.

CONFIDENTIAL

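### Letting the carry-over test choose the primary analysis lifts the type I error of the per-type contrast from 5% to about 6.2-6.3% when there is no carry-over

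*Combined protocol and SAP*

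**What the plan says.** The primary model in section 11.1 has fixed effects of product, product type, period, product by type and period by product. The period-by-product term is there to pick up carry-over, which is assumed equal for 1-piece and 2-piece users. The rule is then: "If the interaction is significant, data from only the first test period will be analysed as a parallel arm study". The reason given is that period 1 cannot contain carry-over.

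The contrasts of interest are per type: "All combinations of differences between the two products will be estimated for both 1- and 2- pc products" (11.1) and "1-pc and 2-pc users will be evaluated separately (in a combined model)" (11.2). Non-significant fixed effects may be removed, and 11.2 foresees pooling in the fallback: "If there are no significant difference between 1- and 2-pc users, 80 subjects (40 in each arm)".

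Section 11.3 gives one level: "A significance level of 5% will be applied". It gives no separate level for the carry-over test and no allowance for the selection. Section 11.2 gives power for the fallback, but only at differences of 1.7 (one type, 20 per arm) and 1.2 (pooled, 40 per arm).

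The protection against carry-over is the steady-state window, which 4.3 says "begins after three weeks of product use as it is anticipated that the skin has adapted to the new product after three weeks".

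**The concern.** A period-1 comparison is unbiased if it is always used. It is not if it is used only when the two sequences happen to differ. The carry-over test compares subjects' totals between sequences, and those totals include period 1. When the test is significant by chance, the randomised groups differ by chance, and the period-1 product difference contains that same imbalance. It is then tested at 5% as though nothing had been selected.

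At stake is whether the primary test has the level that 11.3 states. The other 0-10 endpoints are to be analysed with the same model as the primary endpoint, so they appear to inherit the rule.

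**Working it through.** **Inputs.** From 11.2: SD 1.82; variance split 68% subject, 0% product-by-subject, 32% residual; about three weekly scores per period; 40 completers per type, hence 20 per sequence per type. From 11.3: 5%. Assumed: two-sided tests, a 5% pre-test, complete and balanced data, no true carry-over. Let *k* be the number of weekly scores averaged per period.

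**The plan's own figures first (*k* = 1).**
- Cross-over: SD of the within-subject difference = √(2 × 0.32 × 1.82²) = 1.456. With 40 subjects and a difference of 0.7, paired *t* power is 84.3% (plan: 85%).
- Fallback: 20 per arm at 1.7 gives 82.1% (plan: 82%); 40 per arm at 1.2 gives 83.0% (plan: 83%).

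The inputs are therefore read as the plan used them. These powers correspond to one score per period, so results are shown for *k* = 1 and *k* = 3.

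**Correlation of the pre-test with the period-1 contrast.** Subject variance = 0.68 × 1.82² = 2.252; residual = 0.32 × 1.82² = 1.060. Let ρ = 0.68/(0.68 + 0.32/*k*), which is 0.68 (*k* = 1) or 0.864 (*k* = 3).
- Types pooled: √((1 + ρ)/2) = 0.917 or 0.966.
- One type: the pre-test uses both types and the contrast only one, so divide by √2: 0.648 or 0.683.

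**Type I error of the rule.** The two-period contrast uses within-subject differences and is independent of the pre-test, which uses totals. So

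error = 0.95 × 0.05 + P(pre-test and period-1 test both significant).

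| Contrast | *k* | P(both) | Error of the rule | False positives given a switch, P(both)/0.05 |
|---|---|---|---|---|
| Per type | 1 | 0.0143 | 6.18% | 28.6% |
| Per type | 3 | 0.0158 | 6.33% | 31.5% |
| Pooled | 1 | 0.0313 | 7.88% | 62.7% |
| Pooled | 3 | 0.0379 | 8.54% | 75.7% |

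Simulation of the whole rule with *t* tests (200,000 trials per setting) gives 6.15% and 6.33% per type, and 7.84% and 8.54% pooled. Always using both periods gives 4.9-5.0% per type.

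**Sensitivity.** A 10% pre-test gives 6.7-6.9% per type and 8.7-9.3% pooled. Over ρ from 0.4 to nearly 1, the error is 6.0-6.4% per type and 7.2-9.7% pooled. Integer scores bounded at 0-10 with mean 2.2 give about 6.3% per type.

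**Power at 0.7, no carry-over, per type (simulated).** Both periods against the rule: 85.2% against 83.1% (*k* = 1) and 99.9% against 97.2% (*k* = 3). Period 1 alone has 22-27%.

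**How well the pre-test protects.** Standard error of its contrast = √((4 × 2.252 + 2 × 1.060/*k*) × 2/40) = 0.746 (*k* = 1) or 0.697 (*k* = 3). The plan gives no carry-over size. Assuming 0.7 (the planned difference), power to detect it is 15-17%. Assuming 1.3 (the difference 11.2 reports from CP300), it is 41-45%. For 80% power the carry-over must be about 2.0-2.1 points.

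**If carry-over does persist** (no product effect, per type, simulated false-positive rate, both periods against the rule):

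| Assumed carry-over | *k* = 1 | *k* = 3 |
|---|---|---|
| 0.7 | 32% against 29% | 74% against 64% |
| 1.0 | 57% against 45% | 96% against 70% |
| 1.3 | 80% against 50% | 100% against 57% |

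The two approaches cross at about 0.45-0.5 points (*k* = 1) or 0.30-0.35 (*k* = 3).

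**The case against.** The strongest reply has three parts.

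- **The excess is small, on a level the plan hardly protects.** Section 11.1 calls the study exploratory and adjusts for no multiplicity; 11.4 counts one significant skin endpoint as success. Unadjusted multiplicity is a separate and larger source of false positives. This stands as a limit on seriousness. It does not make this test a 5% test.
- **The rule is pre-specified and its fallback is powered.** This is true: 11.2 covers the case "If a carry-over effect is present and therefore data from only the first period is analysed as a parallel arm trial 40 subjects", and its 1.7 and 1.2 show that the fallback is imprecise. The effect on type I error is not stated anywhere.
- **Dropping the rule may be worse.** The plan describes no washout, so carry-over is a live possibility, and the last table shows the rule giving fewer false positives once carry-over is appreciable. This stands, and the fix must say so. Neither approach controls error in that range.

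A reader might infer two stronger points that the documents do not support.

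- **That 11.1 contradicts 4.3.** Section 4.3 says: "The statistical analysis will evaluate if there are signs of a carry-over effect and take that into consideration when presenting the results". That is a general statement, and the detailed rule in 11.1 is compatible with it.
- **That the primary estimate is usually badly off.** The mean absolute error of the per-type period-1 estimate is 0.81-0.87 points, but only in the roughly 5% of no-carry-over trials that switch. Over all such trials it is about 0.22 under the rule against 0.18 with both periods (*k* = 1), or 0.14 against 0.11 (*k* = 3). The conditional figure should not be set beside the planned 0.7 as if it were typical.

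**Conclusion.** The point holds as a modest failure to meet a stated level, and it should be fixed. The per-type figure, an excess of about 1.2-1.3 percentage points, is the one to quote, because that is the contrast the plan estimates and powers. The pooled figure applies only if the model is reduced, which 11.1 and 11.2 both permit. These are two separate scenarios; neither is the error rate of the whole procedure with its discretionary model reduction.

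The result rests on no true carry-over, the CP300 variance split, balanced and complete data, and a 5% two-sided pre-test, which 11.3 implies but does not state. It says nothing about trial-wide error. Nor does it show that the two-period analysis is better in all circumstances: that depends on whether the skin adapts within three weeks, which the documents anticipate but do not demonstrate.

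**What to change.** In 11.1:

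1. Remove the sentence that lets the interaction p-value select the analysis. Make the two-period steady-state analysis, with period in the model, primary.
2. Always report the product-by-period estimate with its confidence interval, and always report the period-1-only analysis as a sensitivity analysis, noting its low precision.
3. State that the primary result relies on the three-week adaptation anticipated in 4.3. If carry-over persists, the two-period estimate is biased by half of it, and above about 0.3-0.5 points its false-positive rate exceeds that of the present rule.

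If the sponsor prefers to keep the rule, state the level of the pre-test and the operating characteristics of the two-stage procedure, and do not describe the primary test as a 5% test.

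The cost is wording only; sample size and data collection do not change. What is given up is the partial protection that the rule offers when carry-over is large. The added reporting does not replace it: comparing the period-1 and two-period estimates detects carry-over no better than the pre-test does.
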